4.2 Study Endpoint

4.2.1 Primary Endpoint

The primary efficacy endpoint is the proportion of index subjects who are lice free (defined as no live lice, adults or nymphs) 14 days (Day 15) after treatment.

4.2.2. Secondary Endpoint

The secondary efficacy endpoint is the number and percentage of all index subjects who are lice-free at Day 2.

5 Study Enrollment and Withdrawal

5.1 Inclusion Criteria

In order to be eligible to participate in this study, an individual must meet ALL of the following criteria:

- 1. Subjects must have an active head lice infestation defined as: At least 3 live lice (adults and/or nymphs) present on the scalp and/or hair, as determined by a trained evaluator. The index subject must be the youngest family member, through the age of 18, presenting with an active head lice infestation.
- 2. Household members that have an active head lice infestation defined as: At least 1 live louse (adult and/or nymph) present on the scalp and/or hair, as determined by a trained evaluator (with the exception of the male head of household who may self-assess as being lice free) will receive the Standard of Care with an over-the-counter head lice treatment product. Up to 3 infested household members may receive treatment, if more than 3 household members are infested, the entire household will be excluded from the study.
- 3. Subject is male or female.
- 4. Index subject is at least 6 months through 18 years of age at time of enrollment.
- 5. Subject is in good general health based on medical history.
- 6. Each subject must have an appropriately signed Informed Consent agreement. A caregiver must sign an Informed Consent agreement for children not old enough to do so. Children 6-17 years of age will be administered a child's Assent Form.
- 7. The caregiver of a subject must be willing to allow all household members to be screened for head lice. If other household members are found to have an active head lice infestation, they must be willing and able to participate in receiving the Standard of Care. No more than one working male per household may be excluded from evaluation if he is assessed as being lice free by himself or the caregiver and cannot come in due to his work schedule. If this individual may have lice, he must come to the test facility; otherwise the entire household will be excluded from study participation.
- 8. Subject and/or their caregiver must be physically able and willing to apply the test product according to established treatment methods.
- 9. Subject agrees not to use any other form of lice treatments (commercial, community-anecdotal, or mechanical/manual) while participating in the study.

Protocol Number: MAP-7189

Version 1.3; 28 December 2017

- 10. Following application and rinsing of the test product, subject agrees not to shampoo, wash, or rinse their hair or scalp until the 24-hour post-treatment evaluation has been completed.
- 11. Subject agrees to not cut or chemically treat their hair while participating in the study.
- 12. Subject agrees to follow all study instructions, including attending all follow-up appointments.
- 13. Female index subjects of childbearing potential must be willing to have a urine pregnancy test prior to inclusion in this study.
- 14. In the event of a subject judged to be incapable of self-treating, the household must have a caregiver willing to apply the treatment at home.

5.2 Exclusion Criteria

An individual who meets any of the following criteria will be excluded from participation in this study:

- 1. Index subjects with greater than 3 household members with at least 1 live louse (adult and/or nymph) present on the scalp and/or hair, as determined by a trained evaluator will be automatically excluded from the trial.
- 2. Youngest household member is over 18 years of age.
- 3. History of irritation or sensitivity to ivermectin or the lotion components, pediculicides or hair care products.
- 4. Presentation at the treatment site with visible skin/scalp condition(s) that are not attributable to head lice infestation, such as an erythema score that is >2, blisters, vesicles which, in the opinion of the investigative personnel or medical monitor, will interfere with safety and/or efficacy evaluations.
- 5. Presentation at the treatment site with eczema or atopic dermatitis.
- 6. Treatment for head lice (Over the counter [OTC], home remedy and/or Prescription) in the last 15 days.
- 7. Any condition or illness that, in the opinion of the investigator, may compromise the objective of the protocol.
- 8. Is receiving any other treatment which, in the opinion of the investigator or medical monitor, may interfere with the study results.
- 9. Females (including caregivers who come in contact with the investigational product) who are pregnant, nursing or planning a pregnancy which could include index subjects. If a household has a pregnant female who has an active case of lice, the entire household is excluded from participation. If this pregnant household member does not have an active infestation, this individual must NOT be the caregiver (one who provides treatment to other household members).
- 10. Is of child-bearing potential, including index subjects, and unwilling to use an adequate method of contraception for the duration of the study. Adequate methods of contraception include: abstinence, vasectomized partner, oral birth control pills, birth control injections or patches, Intra uterine devices, condoms with a spermicidal jelly or a diaphragm with spermicidal jelly, surgical sterilization. Index subjects and/or caregivers will be considered non-child-bearing if the following has occurred: full hysterectomy or

bilateral oophorectomy is considered surgically sterile. Tubal ligation is not considered equivalent to female sterilization.

- 11. Participation in a previous investigational drug study within the past 30 days.
- 12. Does not understand the requirements for study participation and/or may likely exhibit poor compliance, in the opinion of the investigator.
- 13. Does not have a known household affiliation with their household members (i.e., do not stay in one household consistently, sleeping at one place several nights and then at another place or location). Household is defined as living in a shared area or space (for example the same house or apartment unit). [6]

5.3 Criteria for Inclusion of Minor Subjects

Subjects aged 6 years through 17 years of age must sign the Assent Form that will be written in such a way as to be understandable to a child and to obtain parental or legal guardian consent prior to enrollment in this study.

5.4 Strategies for Recruitment and Retention

- Expected total number of screened subjects will be 311.
- Given a 10% screen failure rate, an anticipated number of enrolled subjects will be 280.
- Assumed dropout rate is 10%, therefore an expected number of 252 subjects will complete the study.
- Source of subjects will be primarily from area schools, along with referrals by local pediatricians to these participating, dedicated clinical lice centers.
- Retention of subjects will be supported by thorough visit reminders and proper education on the study itself, including study duration, activities and responsibilities.
- Approximately 6 geographically diverse clinical research centers in the US will be participating.

5.5 Subject Withdrawal and Termination

5.5.1 Potential Reasons for Withdrawal

In accordance with the Declaration of Helsinki and other applicable regulations, a subject has the right to withdraw from the study at any time and for any reason without prejudice to his or her future medical care. The Investigator or Medical Monitor may also withdraw the subject at any time if it is medically necessary or in the interest of subject safety.

A subject will be discontinued from this study if any of the following criteria are met:

- Withdrawal of consent by the subject is received.
- In the opinion of the Investigator or Medical Monitor it is not in the subject's best interests to continue in the study.
- Occurrence of an Adverse Event (AE) or Serious Adverse Event (SAE), which, in the opinion of the Investigator, warrants discontinuation of the subject from the study.
- Pregnancy as informed by the subject or as determined by a positive urine pregnancy test.

- Significant non-compliance with study procedures that would interfere with the study results or increase the subject's risks in the study, as determined by the Investigator.
- Subject is deemed to be a treatment failure if upon revisit it is determined that they are still infested. They will be terminated from the study and provided the standard of care at that point in the study.
- Any clinical adverse event (AE), laboratory abnormality, or other medical condition or situation occurs such that continued participation in the study would not be in the best interest of the participant
- The participant meets an exclusion criterion (either newly developed or not previously recognized) that precludes further study participation.

5.5.2 Handling of Subject Withdrawals or Termination

The Sponsor reserves the right to discontinue the trial prior to inclusion of the intended number of subjects. After such a decision, the Investigator must contact all participating subjects within a time period specified by the Sponsor to inform them of the decision to discontinue the trial.

5.6 Premature Suspension or Termination of Study

The following criteria may result in either temporary suspension or early termination of the study:

- New information regarding the safety or efficacy of the investigational product that indicates a change in the known risk/benefit profile for the compound, such that the risk/benefit is no longer acceptable for subjects participating in the study.
- Significant violation of GCP that compromises the ability to achieve the primary study objectives or compromises subject safety.

The Sponsor reserves the right to discontinue the trial for other valid administrative reasons.

Criteria for Premature Termination or Suspension of Investigational Sites:

 A study site may be terminated prematurely or suspended if the site (including the Investigator) is found to be in significant violation of GCP, protocol, contractual agreement, or is unable to ensure adequate performance of the study.

Procedures for Premature Termination or Suspension of the Study or Investigational Site(s):

- In the event that the Sponsor elects to terminate or suspend the study or the participation of an investigational site, a study-specific procedure for early termination or suspension will be provided by the Sponsor; the procedure will be followed by applicable investigational sites during the course of termination or study suspension.
- Appropriate therapy and follow-up should be ensured for any study subject by the sponsor.
- Ensure where required by applicable regulatory requirements that the regulatory authority is properly informed.
- If the sponsor terminates the study or the subject withdraws, the end of treatment visit and/or discontinuation visit should be conducted.

6 Study Drug

6.1 Study Agent (s) and Control Description

6.1.1 Acquisition

The drug depot will receive study agents and perform IP accountability and monitoring, including assurance of adequate contents and quantities, based upon the IP packing list. For acquisition of study agents at the clinical sites, study agents will be shipped to each individual clinical site through the designated drug depot. The drug depot will provide initial study agents for study initiation and resupply thereafter, as needed.

6.1.2 Formulation, Appearance, Packaging and Labeling

6.1.2.1. Reference Product

The reference product Sklice®, marketed by Arbor Pharmaceuticals, is supplied in 4 oz. tubes. It is an off-white/tan lotion. The formulation composition Sklice® consists of the following ingredients according to the FDA-approved labelling:

Study agent lotion: 0.5%; each gram of lotion contains 5 mg of ivermectin active ingredient.

Inactive ingredients: water, olive oil, oleyl alcohol, Crodalan AWS, lanolin alcohol, cyclomethicone, shea butter, sodium citrate, sorbitan tristearate, methylparaben, propylparaben, and citric acid.

6.1.2.2. Test

The test product is Ivermectin Lotion 0.5% manufactured by Mayne Pharma International Pty Ltd., supplied in 4 oz. tubes. It is a white to off-white lotion. The formulation composition of the test product consists of the following ingredients:

Study agent Lotion: 0.5%; each gram of lotion contains 5 mg of ivermectin active ingredient.

Inactive ingredients: Medium Chain Triglycerides, Carbomer Homopolymer, Polyoxyl 50 Stearate, Glyceryl Monostearate, Propylene Glycol, Paraffin Liquid, Methyl Hydroxybenzoate, Propyl Hydroxybenzoate, Citric Acid Anhydrous, Sodium Citrate, Triethanolamine, Sodium hydroxide, Purified water.

6.1.3 Product Storage and Stability

Store at room temperature 20°C to 25°C (68°F to 77°F); excursions permitted to 15° to 30°C (59°F to 86°F). Do not freeze. All study drug supplies will be kept in a secure cabinet or room with controlled access. Only the designated study personnel will have access to study drug supplies.

The Investigator will maintain temperature monitoring of the study drug with daily temperature readings. All temperature excursions must be reported to the Sponsor using the Temperature Excursion Form. If the study drug was exposed to the temperature excursion outside the range 15-30°C, or within this range, but for the period greater than 24 hours, the study drug must be quarantined until the Medical Monitor / Sponsor's approval on future use. Please refer to the Pharmacy Manual for additional detail on the Temperature Excursions and temperature monitoring during the shipment and storage at the site pharmacy.

6.1.4 Preparation

Ivermectin 0.5% lotion requires no preparation prior to use.

6.1.5 Dosing and Administration

Apply full tube amount (4 oz.) to dry hair to completely cover the scalp and hair for index subjects ages 5 and older. For babies, please apply 1 oz. of product, equivalent to $\frac{1}{2}$ of the study tube amount. For toddlers, please apply 2 oz., equivalent to $\frac{1}{2}$ of the study tube amount. Apply closest to the scalp first, and then apply outwards towards the ends of the hair.

Leave on the hair and scalp for 10 minutes, and then rinse off with water.

The tube is intended for single use, do not retreat.

Keep out of reach of children. Use on children should be under the direct supervision of an adult.

Avoid contact with eyes. Do not swallow. Thoroughly wash hands after applying lotion.

Ivermectin lotion should be used in the context of an overall lice management program:

- Wash (in hot water) or dry-clean all recently worn clothing, hats, used bedding and towels.
- Wash (in hot water) personal care items such as combs, brushes and hair clips.
- A fine-tooth comb or special nit comb may be used to remove dead lice and nits, as recommended per the FDA Guidance on the treatment of Head Lice.

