CFR	Code of Federal Regulations
CMP	Clinical Monitoring Plan
CRA	Clinical Research Associate
CRF	Case Report Form
CRO	Contract Research Organization
eCRF	Electronic Case Report Forms
EOS	End of Study
ET	Early Termination
FDA	Food and Drug Administration
GCP	Good Clinical Practice
IB	Investigator's Brochure
ICF	Informed Consent Form
ICH	International Conference on Harmonisation
IEC	Independent Ethics Committee
IMV	Interim Monitoring Visit
IRB	Investigational Review Board
ITT	Intent to Treat
LOCF	Last Observation Carried Forward
Mayne	Mayne Pharma, LLC/ Mayne Pharma International Pty Ltd
MedDRA	Medical Dictionary for Regulatory Activities
mITT	Modified Intent-to-Treat
MRT	Mean Residence Time
ОТС	Over the Counter
PI	Principal Investigator
PMH	Past Medical History
PP	Per-Protocol
QA	Quality Assurance
QC	Quality Control
SAE	Serious Adverse Event
SAP	Statistical Analysis Plan
SAS	Statistical Analysis System
SD	Standard deviation
SOC	System Organ Class
SOP	Standard Operating Procedure
SUSAR	Suspected Unexpected Serious Adverse Event
TEAE	Treatment Emergent Adverse Event
US	United States
WHO	World Health Organization

INVESTIGATOR SIGNATURE PAGE

The signature below constitutes approval of this protocol and provides the necessary assurance that this study will be conducted at his/her investigational site according to all stipulations of the protocol including all statements of confidentiality and in accordance with International Conference on Harmonisation (ICH) Good Clinical Practice (GCP) and local regulatory requirements.

Print Name	
Title	
Address of Institution / Site	
Telephone Number:	
INVESTIGATOR SIGNATURE:	DATE:

Synopsis

Study Title A Randomized, Multi-Center, Double-blind, Placebo Controlled, Parallel Group Trial to

Evaluate Efficacy and Safety of Mayne Pharma's Ivermectin 0.5% Lotion Compared to

Sklice® 0.5% Lotion in the Treatment of Head Lice

Protocol Number MAP-7189

Development Phase 3

Type of Study Clinical Endpoint Bioequivalence

Test Product Ivermectin 0.5% Lotion

Sklice® 0.5% Lotion

Placebo Lotion

Name of Active Ingredient

Ivermectin

Route, Dose and Dosage Regimen

Route: Topical application

Dose: Apply full tube amount (4 oz.) to dry hair to completely cover scalp and hair. Apply closest to the scalp first, and then apply outwards towards the ends of the hair.

Regimen: One 10-minute application then thoroughly rinse with warm water

Sponsor Mayne Pharma, LLC

Greenville, NC, USA

Study Objectives

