2.1 Background Information

The head louse, or *Pediculus humanus capitis*, is a wingless, parasitic insect that can be found on the head, eyebrows, and eyelashes of people. Head lice feed on human blood several times a day and live close to the human scalp.

Head lice are found worldwide. In the United States, infestation with head lice is most common among pre-school children attending child care, elementary schoolchildren, and the household members of infested children. Although reliable data on how many people in the United States get head lice each year are not available, an estimated 6 million to 12 million infestations occur each year in the United States among children 3 to 11 years of age. [1]

Ivermectin is a member of the avermectin class of broad-spectrum antiparasitic agents which have a unique mode of action. Compounds of the class cause death primarily through binding selectively and with high affinity to glutamate-gated chloride channels, which occur in invertebrate nerve and muscle cells. This leads to an increase in the permeability of the cell membrane to chloride ions with hyperpolarization of the nerve or muscle cell, resulting in paralysis and death of the parasite. Compounds of this class may also interact with other ligand-gated chloride channels, such as those gated by the neurotransmitter gamma-aminobutyric acid (GABA). The selective activity of compounds of this class is attributable to the fact that some mammals do not have glutamate-gated chloride channels and that the avermectins have a low affinity for mammalian ligand-gated chloride channels. In addition, ivermectin does not readily cross the blood-brain barrier in humans. [2]

Safety of Ivermectin was evaluated in two pivotal trials. Supportive safety data is also available from five other sponsor-conducted Phase 1 and 2 trials. Adverse events which occurred in less than 1% of subjects included conjunctivitis, ocular hyperemia, eye irritation, dandruff, dry skin, and skin burning sensation. Evaluation of cutaneous safety, scalp irritation (Phases 1, 2, 3) and ocular irritation (Phase 3), did not reveal clinically notable signals. [3]

Long-term studies in animals have not been performed to evaluate the carcinogenic potential of Ivermectin, yet it was found not to be genotoxic in vitro in the Ames test, the mouse lymphoma assay, or the unscheduled DNA synthesis assay in human fibroblasts. [4]

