4.1 Description of the Study Design

This is a Phase 3 Randomized, Multi-Center, Double-blind, Placebo Controlled, Parallel Group Trial to Evaluate Efficacy and Safety of Mayne Pharma's Ivermectin 0.5% Lotion Compared to Sklice® 0.5% Lotion in the Treatment of Head Lice. The subject population includes healthy male and female subjects aged 6 months through 18 years who are infested with *Pediculus humanus capitis*. The youngest infested household member will be considered the index subject. Household members, up to a maximum of 3 members, infested with an active head lice infestation defined as at least 1 live louse (adult and/or nymph) present on the scalp and/or hair, as determined by a trained evaluator will receive treatment with an over-the-counter head lice treatment product at baseline.

The planned overall sample size for this clinical trial is approximately 280 index subjects, who will be randomized at different geographical clinical research centers in the United States.

Potential subjects will be screened and the index subject will be eligible for enrollment into the study. During the baseline visit (Day 1), which can occur on the same day as screening (Day 0), the Investigator will record subject's demographics, medical history, review concomitant medication, identifying any prohibited therapies the subject may receive, perform physical examination, collect vital signs and perform urine pregnancy test. Eligible subjects will be randomized in a ratio of 3:3:1 to receive either the Mayne Pharma's Ivermectin 0.5% lotion, Sklice® 0.5% lotion, or placebo lotion treatment and will be trained on the application of the study drug and subject's diary completion. Infested household members, up to 3 members per household, will be treated with an over-the-counter head lice treatment product on-site.

The study drug will be applied as a single, at-home dose. Subjects will be instructed to apply a full tube amount (4 oz.) of Ivermectin 0.5% lotion to fully coat dry hair and scalp, avoiding the eyes and mucus membranes. The lotion will be left on the hair and scalp for 10 minutes, then rinsed off with warm water. The tube is intended for a single use; all used tubes should be returned at the second visit (first follow-up visit) to the clinical site for product accountability. In addition to receiving the study drug, the index subjects and household members will be instructed on an overall lice management program, which includes:

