6.1.9 Tracking of Dose and Treatment Compliance

Subject diaries will be distributed and accounted for, along with return of used test tubes. Subjects will fill out their diaries upon treatment application noting the following:

- Time and date of application
- Time and date of removal (washing off the study drug)
- Confirmation that subject disinfected personal clothes, towels, linens and all potentially infected household items
- Confirmation that the entire scalp and hair has been covered by the application

Subjects will return their diaries to the clinical site for compliance review at Follow-up Day 2. The Investigator will verify that the subject complied with the application requirements and disinfection regimen. Both the subject and the study staff will sign off on completed diary. If the subject has missed the treatment application notation, this is considered a protocol deviation and must be reported.

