10.2 Data Sets to Be Evaluated

The subject populations are defined as follows:

Safety Population includes all subjects who were randomized and dispensed treatment. This is the population that will be used for the safety assessments.

Modified Intent-to-Treat (mITT) population includes all Index subjects who met all inclusion/exclusion criteria, were randomized, dispensed treatment, and had at least one post-treatment efficacy evaluation. This is the primary population for determination of the superiority of the active treatments over placebo.

Per-Protocol (PP) population includes all mITT subjects who applied their dispensed treatment, had no protocol deviations which could have interfered with the accurate assessment of treatment efficacy, and returned for the Day 15 visit within the allowed window. This is the primary population for the efficacy comparisons between the two active treatment groups.

Subjects whose condition worsens and require alternate or supplemental therapy for the treatment of head lice during the study will be discontinued, included in both the mITT and PP population analyses as treatment failures. Subjects who discontinue early for reasons other than treatment failure will be excluded from the PP population, but included in the mITT population, using Last Observation Carried Forward (LOCF).

Efficacy analyses will be performed on both the per-protocol population and the mITT population. Safety analyses will be performed using the Safety population as defined.

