16.2 Subject Diary

Study Title:

Subject Diary

Protocol Number: MAP-7189

A Randomized, Multi-Center, Double-blind, Placebo Controlled, Parallel Group

Trial to Evaluate Efficacy and Safety of Mayne Pharma's Ivermectin 0.5% Lotion Compared to Sklice® Ivermectin 0.5% Lotion in the Treatment of Head Lice

SUBJECT NUMBER:													
BASELINE VISIT DATE:													
	D	D	М	М	М	Y	Y	Y	Y				
To be completed by the study team member & cover page to remain at the site													
	SUBJECT TREATMENT INFORMATION												
Study Visit Visit 2													
		HOUS	SEHOLD I	MEMBER	RS TREATI	MENT INF	ORMATIO	ON					
Number of Infe	ested Ho	usehold	Member	's									
Number of No	n-Infeste	ed House	hold Me	mbers									
Total Number	of House	ehold Me	embers										
Infested House	Infested Household Member # 1 Standard of Care Treatment Yes No												
Infested House	hold Me	ember#	2 Standa	rd of Ca	re Treatm	ent 🗌 Ye	es N	0					
Infested House	Infested Household Member # 3 Standard of Care Treatment Yes No												

SUBJECT NUMBER:							SUBJEC			
VISIT DATE:										
	D	D	М	М	М	Y	Υ	Y	Y	

	APPLICATION OF THE STUDY DRUG		
Activity	Instructions for Application of study drug	Status check	k (Tick)
Application of Lotion	 Apply full tube amount (4 oz.) to fully coat dry hair and scalp for children ages 5 and older For babies, apply 1 oz. (1/4 of a tube) and for toddlers apply 2 oz. (1/2 of a tube). Avoid contact with eyes and mucus membranes Record the date and time the lotion was applied Leave on for 10 minutes 	Date of App	M M Y Y Y Y
AFTER	 After 10 minutes fully rinse lotion off with warm water Record the date and time the lotion was washed off Caregivers to properly wash hands after treatment. 	Date of Ren	M M Y Y Y Y
AFTER (cont.)	Do not shampoo, wash, or rinse hair or scalp until the 24-hour post-treatment evaluation has been completed.	Date to Sha	M M Y Y Y Y
	ASSOCIATED STEPS WITH STUDY TREATM	IENT	
Activity			Status check (Tick)
LAUNDRY DISIN			□vaa □N-
 Wash (in hot towels. 	water) or dry-clean all recently worn clothing, hats, used	bedding &	∐ Yes

•	Wash (in hot water) personal care items such as combs, brushes, & hair clips	

SUBJECT NUMBER:							SUBJEC INITIAL			
VISIT DATE:										
	D	D	М	М	М	Y	Y	Y	Y	

Please answer the following questions by ticking the correct box:

Have you had any health problems since your last visit to clinic?
Yes No If yes, please discuss with Principal Investigator at your next visit.:

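### Children under 5 are given conflicting amounts of study lotion: a full 4 oz tube for everyone in the Synopsis, Section 4.1 and SAP 1.1, but age-dependent amounts with undefined age groups in Section 6.1.5 and the diary

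*Protocol*

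**What the plan says.** Five places state how much lotion to apply.

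- **Synopsis, Route, Dose and Dosage Regimen:** "Dose: Apply full tube amount (4 oz.) to dry hair to completely cover scalp and hair". No age limit is given.
- **Protocol Section 4.1:** "Subjects will be instructed to apply a full tube amount (4 oz.) of Ivermectin 0.5% lotion to fully coat dry hair and scalp". No age limit is given.
- **SAP Section 1.1:** repeats the Section 4.1 sentence, again without an age limit.
- **Protocol Section 6.1.5:** "Apply full tube amount (4 oz.) to dry hair to completely cover the scalp and hair for index subjects ages 5 and older". It then gives 1 oz for babies and 2 oz for toddlers.
- **Subject diary (Section 16.2):** full tube for ages 5 and older, then "For babies, apply 1 oz. (1/4 of a tube) and for toddlers apply 2 oz. (1/2 of a tube".

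On eligibility, Section 5.1 states: "Index subject is at least 6 months through 18 years of age at time of enrollment". Section 4.1 makes the youngest infested member of the household the index subject.

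On compliance, Section 6.1.9 lists four things the family records. These are the time and date of application, the time and date of removal, disinfection of household items, and the following: "Confirmation that the entire scalp and hair has been covered by the application". The amount applied is not among them. The per-protocol population (Section 10.2 and SAP Section 4) is limited to subjects who, among other conditions, "had no protocol deviations which could have interfered with the accurate assessment of treatment efficacy".

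**The concern.** For a child under 5 the instructions cannot all be followed. A site that trains the caregiver from Section 4.1 and then hands over the diary gives two different amounts for the same child. The lotion is applied at home, and the documents describe no check by site staff at the time of application.

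Two things are at stake. The first is that the dosing instruction for the youngest children in the trial must be unambiguous. The second concerns the analysis. The per-protocol population is definitive for bioequivalence, and membership depends on a judgement about deviations. If someone has to decide whether the amount applied was a deviation, the documents do not say which instruction is the standard, and the listed diary items do not record the amount.

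**Working it through.** The plan states no figure to reproduce here. The check sets the instructions side by side and then applies simple arithmetic.

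**1. Amount by age group and source**

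| Age group | Synopsis, 4.1, SAP 1.1 | 6.1.5 and diary | Ratio |
|---|---|---|---|
| Babies (no ages given) | 4 oz | 1 oz | 4 / 1 = 4-fold |
| Toddlers (no ages given) | 4 oz | 2 oz | 4 / 2 = 2-fold |
| Other children under 5, if any | 4 oz | none stated | not applicable |
| Ages 5 and older | 4 oz | 4 oz | no conflict |

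No passage says which text takes precedence. Neither the Synopsis nor Section 4.1 refers to Section 6.1.5 or mentions an amount that depends on age.

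**2. The gap inside Section 6.1.5 and the diary**

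The documents define neither age term, so the size of the gap depends on where *toddler* is assumed to end:

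- at the 3rd birthday: ages 3 and 4 have no amount in these two places;
- at the 4th birthday: age 4 has none;
- at the 5th birthday: no child is left out.

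The boundary between 1 oz and 2 oz is undefined under all three assumptions.

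**3. How much of the eligible age range is affected**

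- Eligible span, 6 months through 18 years (to the 19th birthday): 19 − 0.5 = 18.5 years.
- Under 5: 5 − 0.5 = 4.5 years.
- 4.5 / 18.5 = 24.3% of the age span. This is not a share of subjects.

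**4. How many subjects**

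The documents do not give the share under 5. The group is unlikely to be empty. Section 2.1 says "infestation with head lice is most common among pre-school children attending child care, elementary schoolchildren", and the youngest-member rule favours younger children. Assumed shares, applied to the 280 planned index subjects and to the 108 + 108 = 216 planned per-protocol subjects on active treatment:

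| Assumed share under 5 | Of 280 | Of 216 |
|---|---|---|
| 10% | 28 | 21.6, about 22 |
| 25% | 70 | 54 |
| 40% | 112 | 86.4, about 86 |

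**5. Tube fractions (side check only)**

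Both active products come in 4 oz tubes (Sections 6.1.2.1 and 6.1.2.2). So 1 oz is 1/4 of a tube and 2 oz is 1/2, as the diary says. Section 6.1.5, as extracted from the PDF, gives 1/2 for both. This may be an extraction error, and nothing above depends on it.

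**The case against.** The strongest reply is that the texts closest to the act of dosing agree. Section 6.1.5 is the dosing section, the family takes the diary home, and the two match in ounces. On this view the Synopsis and Section 4.1 are summaries that leave out the age tiers. SAP 1.1 is weaker still, because the SAP introduction calls its design material background and refers the reader to the protocol for study conduct. This stands in part. The SAP text is not a competing instruction to families, and the 4-fold and 2-fold figures are maxima, not the spread to expect. But Section 4.1 states what subjects will be told to apply, and sites work from it. Nothing subordinates it to Section 6.1.5. The undefined age terms also lie within Section 6.1.5 and the diary, so giving those two precedence would not cure them.

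A second reply is that compliance is checked. Used tubes come back at Day 2, all dispensed tubes are accounted for, and Section 6.1.9 has the investigator verify adherence to the application requirements. That is relevant, but no weighing of tubes is stated, and the requirement to be verified is the one in conflict.

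Third, no effect on the conclusions is demonstrated. The instructions are the same for all arms, and randomization is stratified by site. This is correct: no bias between arms is shown, nor that any subject would be excluded on amount.

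Fourth, babies may be few. Section 2.1's infestation estimate is for ages 3 to 11, and Section 5.4 expects recruitment mainly through schools. That is fair, while the youngest-member rule pulls the other way. The share stays unknown, which is why only assumed values are shown.

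Finally, *toddlers* could be read as running to the 5th birthday, leaving no child without an amount. This is possible, but the documents do not say so, and the line between babies and toddlers would still be missing.

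**Conclusion.** The concern holds. For every eligible child under 5, the protocol either states two different amounts of study drug or, depending on how the undefined terms are read, states an amount only in the places that carry no age limit. The difference is at most 4-fold for babies and 2-fold for toddlers; there is none from age 5.

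The contradiction and the missing age definitions rest on the text alone. The subject counts rest on assumed shares of 10% to 40% and show scale only. The per-protocol point is that the compliance standard on amount is unspecified. It is not a claim that the bioequivalence result would be distorted.

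It must be fixed because it concerns what the youngest participants are given and the correction is cheap.

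**What to change.** - Reconcile the Synopsis, Protocol Sections 4.1 and 6.1.5, the diary in Section 16.2, and SAP 1.1 to one instruction. It should cover every age from 6 months through 18 years without gaps or overlaps, and any age group it names should have stated ages. Which amount applies, and whether it varies with age, is for the sponsor's clinical team.
- Check the tube fraction in Section 6.1.5 against the original page, and make ounces and fractions agree wherever both appear.
- State in Section 10.2 and SAP Section 4 that per-protocol compliance on amount is judged against that instruction.
- Preferably, add the amount applied to the diary items in Section 6.1.9 so that it can be judged. The reconciliation does not depend on this.

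The cost is wording changes in the protocol, diary and SAP, site retraining and, if adopted, one diary entry. No extra subjects or visits are needed.
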